9.2.3 Post-intervention PRO assessments

All PRO assessments will be done electronically via REDCap or UW Qualtrics, or on paper at the UWCCC/UWHC. They will require approximately 20 minutes to complete. If the surveys are completed on paper, a member of the study staff will collect the PRO assessments in an opaque-sealed envelope and transport them immediately to the secure locked study office that is administering this study. Surveys will be identified by study ID and date to protect confidentiality of subject. PROs will be completed by the subject prior to vaginal swab/collection.

9.3 Logbooks

The logbooks will be provided to subjects at the baseline visit. We will ask the subject to enter the days they have performed the VRP program during the study. They will also be asked to record the number of days of each week that they did not take their Aromatase Inhibitor. Subjects will be reminded to enter data into this log with phone calls approximately 1 week and approximately 1 month after VRP instruction. Logbooks will be collected from subjects at the study completion visit.

9.4 Study Completion Visit

All subjects will be asked to return 12 weeks (+/- 4 weeks) after in-person instruction of the VRP program. Subjects will complete post-intervention PROs prior to undergoing vaginal swab/collection. Subjects will be asked to bring and turn in the logbooks for analysis.

9.5 Adverse Device Effects

Adverse Device Effects will be reported by the subject or investigator for the duration of the study. Unanticipated adverse device effects will be reported to the appropriate regulatory agencies per section 15.

10.0 MEASUREMENT OF INTERVENTION EFFECT

10.1 Response

A positive response to the VRP intervention will be confirmed if the percentage of superficial vaginal cells changes from $< 2\%$ to $\geq 4\%$ from pre-intervention to post-intervention.

11.0 STATISTICAL METHODS

All statistical analyses will be done by the study biostatistician. A general description of the statistical methods to be used to analyze the efficacy and safety data is outlined below.

11.1. Subject Information

For all subjects who are enrolled in this study, descriptive statistics will be provided.

11.2 Sample Size Determination

The Simon Two Stage design will be utilized for this study. The null hypothesis that the true positive response rate is 10% will be tested against a one-sided alternative using the exact binomial test. The study will be powered to detect a positive response rate of 30% or greater with approximately 80% power and a type I error rate of 5%.

The first stage sample size will be 15 patients. If there are 1 or fewer responses in these 15 patients, the study will be terminated. If the trial goes on to the second stage, a total of 25 patients will be studied (i.e. additional 10 patients will be recruited). The null hypothesis will be rejected if 6 or more responses are observed in 25 patients. We will assess response with a blinded standardized interpretation of superficial vaginal epithelial cells by a board-certified pathologist.

11.3 Primary Endpoint

We expect the percentage of superficial vaginal cells to be greater at the post-intervention time point when compared to the pre-intervention time point. If the percentage of superficial vaginal cells is $\geq 4\%$ following the intervention, then the response will be considered positive.

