3.0 STUDY DESIGN OVERVIEW & RATIONALE

We will utilize a prospective Simon two-stage Phase II study design. Breast cancer patients who have completed primary active therapy for breast cancer (e.g. surgery, chemotherapy and/or radiation) and are currently taking maintenance aromatase inhibitors (AIs) such as anastrozole, letrozole or exemestane will be approached. We will assess response to the VRP with a blinded standardized interpretation of superficial vaginal epithelial cells. Entrance criteria will stipulate baseline measurements must be < 2%. If the subject has $\geq 4\%$ superficial vaginal cells on cytologic evaluation after the intervention period, then the response will be considered positive.

After documentation of eligibility according to the inclusion and exclusion criteria (**see Section 5.0**) and after enrollment, the subject will receive instruction in the VRP (**see Section 6.0** for details and **Study Schema**). Baseline demographic data, baseline vaginal cell cytology, vaginal pH, and PROs will be collected prior to initiating the VRP instruction. During the time on study, subjects will log their adherence to the prescribed therapy schedule of the VRP and AI therapy. Subjects will receive reminder contacts from study staff/team member 1 week and 1 month after initial instruction. These calls will function to ensure that subjects have had adequate instruction, and problem-shoot any issues with adherence to the program and logging adherence. The subject will return the journal at the 12-week study completion visit when vaginal cell cytology, vaginal pH, and PROs will be assessed.

The primary endpoint of percent superficial vaginal cells will be determined via blinded review by a board-certified pathologist experienced with interpretation of cytology. Secondary endpoints of pH will be logged at the time of the exams and PROs will be determined by standardized, validated scoring metrics for the respective PRO measures used. The exploratory analysis of AI adherence will be determined using patient-reported logs.

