9.2.1 Post-intervention cytology collections

A clinician trained in the collection of lower female genital tract cytology specimens will collect the cytology. The amount collected will be equivalent to a routine PAP test. The cytology specimen will be transported to the pathology department and stored as documented in **Section 9.1.1**. At the completion of each stage of the study, all pre-intervention cytology collections and post-intervention cytology collections will be pooled and interpreted with the specimens blinded as to the timing of the collections.

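### Section 11.3 scores response on the post-intervention slide alone, 10.1 needs both slides, and the plan does not secure the below-2% baseline that would make them agree

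*Combined protocol and SAP*

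**What the plan says.** **Two statements of the responder rule.** Section 10.1 uses both slides: "A positive response to the VRP intervention will be confirmed if the percentage of superficial vaginal cells changes from" below 2% to 4% or more. Section 11.3, which defines the primary endpoint for analysis, sets only the later condition: if the value is at least 4% "following the intervention, then the response will be considered positive".

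**Section 3.0.** Its 4% sentence also ends on the later value ("after the intervention period, then the response will be considered positive"), but the sentence just before it makes a baseline below 2% a condition of entry. Read together, the two sentences give the 10.1 rule.

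**Entry.** Criterion 5.1.7 requires fewer than 2% superficial cells. Section 3.0 places VRP instruction after eligibility has been documented.

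**When slides are read.** Section 9.1.1 has all slides relabelled at random at the end of the study and interpreted after that. Section 9.2.1 says that at the completion of each stage "all pre-intervention cytology collections and post-intervention cytology collections will be pooled and interpreted with the specimens blinded as to the timing of the collections". No earlier screening read is described. Appendix 1 takes the baseline swab at enrolment and allows enrolment and VRP instruction to share a visit.

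**Who is analysed.** Section 8.2 analyses every enrolled woman who is not lost to follow-up.

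**Decision rules (11.2).** "If there are 1 or fewer responses in these 15 patients, the study will be terminated". "The null hypothesis will be rejected if 6 or more responses are observed in 25 patients".

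**The concern.** A responder rule that looks only at the later slide relies on eligibility to supply the baseline half of the definition. That works only if eligibility is settled on the same reading that feeds the endpoint. Here the baseline slide appears to be read for the first time after treatment, mixed with the post-intervention slides. If it then reads 2% or more, the woman is already enrolled, treated and in the analysis set, and the plan does not say how to score her.

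The decision limits are small counts, so one woman can matter. Suppose five women move from below 2% to at least 4%, and a sixth reads 5% and then 4%. Section 11.3 gives 6 of 25 and rejects the null; 10.1 gives 5 of 25 and does not. At stage 1, one true responder plus one such woman is 2 of 15 (continue) under 11.3 and 1 of 15 (stop) under 10.1. With a single arm, no control group would show how many positives were present before treatment.

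**Working it through.** **Inputs from 11.2.** Null rate 10%, alternative 30%, 15 patients then 25 in total, stop at 1 or fewer of 15, reject at 6 or more of 25; stated type I error 5% and power about 80%.

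**Step 1: reproduce the design.** For a counted response rate p,

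P(success | p) = Σ (x = 2 to 15) C(15, x) p^x (1 − p)^(15 − x) × P[Bin(10, p) ≥ max(0, 6 − x)].

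At p = 0.10 this is 0.0328, within the 5% limit. At p = 0.30 it is 0.8017. The plan's figures reproduce.

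**Step 2: where the two rules differ.** If the baseline is below 2% on the endpoint read, a post value of at least 4% is necessarily a rise of more than 2 points, and both rules classify the woman alike. They differ only when the blinded baseline is 2% or more and the post value is at least 4%:

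| Blinded baseline | Post | 11.3 | 10.1 |
|---|---|---|---|
| 1% | 4% | responder | responder |
| 3% | 4% | responder | non-responder |
| 5% | 4% | responder | non-responder |

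**Step 3: can the last two rows reach the analysis?** Criterion 5.1.7 is meant to keep them out. But 9.1.1 and 9.2.1 place the reading of baseline slides after treatment, no screening read is described, instruction may happen at the visit where the swab is taken, and 8.2 keeps everyone not lost to follow-up. As written, they can.

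**Step 4: illustrate the size.** Assume each woman has probability f of reading at least 4% at both visits, and that the rest respond at 10%. The documents do not give f. The counted rate is then

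- under 11.3: p = 0.10(1 − f) + f = 0.10 + 0.90f;
- under 10.1, with these women kept as non-responders: p = 0.10(1 − f).

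For f = 4%, 0.10 + 0.90 × 0.04 = 0.136 and 0.10 × 0.96 = 0.096. For power under 10.1, let the same share be non-responders and the rest respond at 30%: p = 0.30(1 − f), which is 0.288 at f = 4%. Putting each p into the Step 1 formula gives:

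| f | p, 11.3 | P(success), 11.3 | p, 10.1 | P(success), 10.1 | Power, 10.1 |
|---|---|---|---|---|---|
| 0 | 0.100 | 3.28% | 0.100 | 3.28% | 80.17% |
| 2% | 0.118 | 6.52% | 0.098 | 3.01% | 78.33% |
| 4% | 0.136 | 11.24% | 0.096 | 2.75% | 76.39% |
| 10% | 0.190 | 33.06% | 0.090 | 2.07% | 69.90% |

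Under 11.3 the 5% limit is passed by f = 2%. A share of 4% is one woman in 25. The model leaves out women such as the 3%-to-4% case, whom 11.3 also counts and 10.1 does not. For power, the relevant share is all women with a blinded baseline of 2% or more, which is at least as large as f.

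**The case against.** The strongest reply is that 5.1.7 and the entry sentence in 3.0 already require a baseline below 2%, so 11.3 had no need to repeat it. For every woman who meets 5.1.7 on the endpoint read this is right: the wording difference has no effect, and type I error and power stay at 3.3% and 80.2%.

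Three stronger readings are tempting and are not supported:

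- *That 3.0 contradicts 10.1.* It does not, once its 4% sentence is read with the one before it.
- *That the wording of 11.3 by itself lets an unchanged or falling value count as a response.* It does so only for a woman whose blinded baseline contradicts an entry criterion.
- *That the trial's type I error is 11% or 33%.* Those figures rest on an assumed f. Entry requires at least 6 months of AI therapy, at least 12 months of amenorrhea and no estrogen within 6 months, so the population is chosen to be atrophic and f may be small or zero. It is also zero if every woman with a high baseline reads below 4% afterwards.

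What the reply does not answer is how 5.1.7 is verified. An unwritten screening read may exist, but the pooled blinded read would then be a second reading of the baseline slide and could disagree with it. The plan has no rule for that case.

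**Conclusion.** The concern holds in a conditional form. Section 11.3 omits the baseline condition that 10.1 states, and the plan does not ensure that the omission is harmless, because the reading that would establish a baseline below 2% is described only after treatment. If all blinded baselines are below 2%, the effect is nil. If some are not, the two sections can give opposite conclusions from the same slides. In the illustration, the chance of a false success under 11.3 rises from 3.3% to 6.5%, 11.2% or 33.1% at assumed shares of 2%, 4% or 10%. These figures assume independent women, a 10% response rate in the rest and no real change in the affected women. The sample-size calculation itself is correct.

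**What to change.** 1. Replace the rule in 11.3 with the 10.1 rule: below 2% on the pre-intervention slide and at least 4% on the post-intervention slide, both from the pooled blinded read. A blinded baseline of 2% or more then cannot count as a response.
2. List women with such baselines separately, and state before any pooled read whether they stay in the counts of 15 and 25.
3. Reconcile 5.1.7 with 9.1.1 and 9.2.1: say when, and on which read, eligibility is verified. Settle end of study against end of each stage as well, since the stage 1 rule needs responses after the first 15 women.

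This costs wording only, plus a screening read if one is added. If all baselines are below 2%, nothing else changes. If affected women stay in the denominator as non-responders, power at a 30% rate in the rest falls from 80.2% to 76.4% with 4% affected, or 69.9% with 10%. The type I error stays below 5%.

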11.4 Secondary Endpoint

Changes in the vaginal pH will be analyzed to determine the extent to which the changes correlate with changes in the primary outcome and with patient reported outcomes. Given the longitudinal nature of the study, linear and generalized linear mixed effects models will be fit to the data gathered. The restricted maximum likelihood (REML) criterion will be used and 95% semi-parametrically bootstrapped confidence intervals will be obtained for all parameters. All statistical analyses will be conducted using R (R Core Team 2014).

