2.3 Secondary Objectives

2.3.1 To evaluate changes in vaginal pH from the baseline time point to 12 weeks after initiating the VRP in the same patient population.

2.3.2 To evaluate changes in patient-reported outcomes (PROs) (**see SECTION 9.1.3**) in the same population between the baseline time point to 12 weeks after initiating the VRP.

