5.0 SUBJECT ELIGIBILITY

5.1. Inclusion Criteria

Each potential subject must satisfy all of the following criteria to be enrolled in the study:

_____ **5.1.1** Females \geq age 18 diagnosed with Stage 0-3 breast cancer

_____ **5.1.2** Have completed active primary treatment

- Defined as surgery, chemotherapy and/or radiation for the treatment of breast cancer
- Does not include immunotherapy or other targeted therapies such as trastuzumab, CDK 4/6 or mTOR inhibitors

_____ **5.1.3** Have been receiving AIs for at least 6 months prior to enrollment

_____ **5.1.4** Plan to continue AIs for an additional 3 months

_____ **5.1.5** Amenorrhea for at least 12 months at enrollment regardless of cause

_____ **5.1.6** Participants must be able to read and write in English

_____ **5.1.7** Participants must have < 2% superficial vaginal cells on cytologic evaluation

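### Section 11.4 asks how changes in pH, cytology and PROs go together, but does not say how its mixed models isolate within-woman change; the default form would not

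*Combined protocol and SAP*

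**What the plan says.** Section 11.4 (Secondary Endpoint) sets the question: pH changes are to be analysed to "determine the extent to which the changes correlate with changes in the primary outcome and with patient reported outcomes". For the method it appeals to the longitudinal design and says that "linear and generalized linear mixed effects models will be fit to the data gathered", using REML, and that "95% semi-parametrically bootstrapped confidence intervals will be obtained for all parameters". It does not name the outcome, the covariates, a visit term, the random effects, a change score, or any split between within-woman and between-woman association.

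Section 2.3 limits the data to two times. The pH objective is "To evaluate changes in vaginal pH from the baseline time point to 12 weeks after initiating the VRP", and the PRO objective concerns change "in the same population between the baseline time point to 12 weeks after initiating the VRP". The schedule in Appendix 1 agrees: cytology, pH and PROs are each collected once before the program and once at the 12-week visit. Section 11.5 adds only descriptive summaries for PROs. One entry criterion in section 5.1 bears on the point: "Participants must have < 2% superficial vaginal cells on cytologic evaluation". There is no matching restriction on pH or PRO scores.

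**The concern.** The question is about change. Does a woman whose pH falls over 12 weeks also gain superficial cells or report fewer symptoms? The usual mixed model for such data regresses one variable on the raw value of the other at the same visit, with a random intercept per woman. It returns a single slope that averages two different things: the change-on-change slope within women, and the slope across women, which reflects whether women with higher pH have worse scores at any time.

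If that cross-sectional link exists before anyone uses the VRP, the single slope picks it up. It could then be reported as improvement in pH tracking improvement in symptoms when the data show no such thing. The planned bootstrap does not repair this, because it measures uncertainty around the blended slope and does not move it to the within-woman value.

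**Working it through.** **Plan's own figures.** Section 11.4 gives none. The sample sizes come from section 11.2: "The first stage sample size will be 15 patients", 25 in total, stop at 1 or fewer responses, reject at 6 or more. The exact two-stage binomial calculation gives type I error 3.28% at a 10% response rate and power 80.2% at 30%, which agrees with the plan. The chance of stopping at 15 when the true rate is 10% is 0.9^15 + 15 × 0.1 × 0.9^14 = 0.206 + 0.343 = 54.9%. The secondary analysis may therefore rest on 15 women.

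**Why the default slope is a blend.** Take y(i,t) = a + g·visit + b·x(i,t) + u(i) + e(i,t) with two visits. Let both variables have variance 1 and the same intraclass correlation (ICC), let r be the correlation of women's underlying levels, and let the changes be unrelated.

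- The within-woman slope is 0, which is the true answer.
- The between-woman slope, from each woman's mean, is 2·ICC·r / (1 + ICC).
- Each part is weighted by its sum of squares in x divided by its residual variance in y. To a first approximation this is (1 − ICC)/(1 − ICC) = 1 for the within part and (1 + ICC)/(1 + ICC) = 1 for the between part, so about half the weight goes to each.

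At ICC 0.5 and r = 0.5 the between slope is 2 × 0.5 × 0.5 / 1.5 = 0.33, and half of that is 0.17. At ICC 0.7 it is 2 × 0.7 × 0.5 / 1.7 = 0.41, and half is 0.21. Simulated mean slopes over ICC 0.5 to 0.7 were 0.18 to 0.23 SD per SD in size, close to these values. The true value is 0.

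**How often it misleads.** Simulated two-visit data, changes unrelated, REML fit with a visit term, two-sided 5% t test of b, 2,000 trials per scenario. The documents give neither ICC nor r, so both are assumptions shown as ranges. In the table r was negative; the sign does not matter.

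| Women | ICC | r = 0 | 0.3 | 0.5 | 0.7 |
|---|---|---|---|---|---|
| 25 | 0.3 | 5.9% | 9.3% | 16.3% | 23.7% |
| 25 | 0.5 | 6.0% | 13.5% | 25.9% | 46.3% |
| 25 | 0.7 | 5.5% | 16.3% | 37.3% | 70.1% |
| 15 | 0.5 | 8.1% | 9.6% | 18.1% | 32.8% |

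A repeat over the same ICC range at 25 women gave about 5%, 9-14%, 12-34% and 23-67%. The overall ranges at 25 women are therefore about 5-6%, 9-16%, 12-37% and 23-70%.

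The value r refers to underlying levels. The correlation seen at a single visit is ICC × r: 0.5 × 0.5 = 0.25 in the middle of the table and 0.7 × 0.7 = 0.49 at its extreme.

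**Entry rule.** Truncating baseline y to mimic the cytology criterion (ICC 0.5, r = 0.5 in size, 25 women, 1,000 trials) lowered the rate from 26.6% to 19.2% with a cut at the mean and to 15.3% with a cut 0.5 SD below it. The excess is smaller but not gone. The pH-PRO analysis has no such restriction on either variable.

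**Comparator.** The Pearson correlation of the two change scores in the same data gave 4.0% to 6.2% throughout, with mean correlation about 0. With two complete visits and a visit term, the within-woman slope from a split mixed model is the slope of change on change, so it tests the same thing.

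**The case against.** The strongest reply is that section 11.4 does not contain the faulty model. A reader might infer that the plan commits to a blended slope, or that mixed models are the wrong class of method. The documents support neither. The specification is left open, and a model that splits each covariate into woman mean and deviation, or a bivariate model with separate between-woman and within-woman covariances, would answer the question and is not ruled out.

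The mixed model may also be meant only for the pH change in objective 2.3.1, with visit as the fixed effect. That is a fair reading, but it leaves the correlation question with no stated analysis, so the same sentence is needed.

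Other parts of the reply stand:

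- The rates depend on assumed ICC and r. With uncorrelated levels and a visit term there is no material excess at 25 women.
- The entry rule weakens the effect for cytology.
- Section 11.4 attaches the word changes explicitly only to the primary outcome, not to the PROs, although objective 2.3.2 frames PROs as change.
- The plan calls for estimates with intervals, not a test. The t test was supplied for this check, and the bootstrap intervals were not simulated.

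A reader might also assume that the visit term would be left out. In that case a common 1 SD shift in both variables gives 57.1% at 25 women even with r = 0. This stacks a second unstated choice on the first, and the conclusion here does not rely on it.

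**Conclusion.** The point holds as a gap in specification with a real consequence: the method named does not by itself answer the question asked, and its most usual form answers a different one. How far that misleads depends on how strongly women's underlying levels of pH, cytology and symptoms are related, which the documents do not say. The effect ranges from nothing material to a majority of trials at the most extreme assumed values, and it would be smaller for cytology than for PROs. The analysis is secondary, so the response rule and the two-stage decision in section 11.2 are untouched. It merits correction before analysis because the better method is plain and uses the same data.

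**What to change.** In section 11.4, make the stated analysis the correlation of 12-week minus baseline changes: pH with percent superficial cells, and pH with each PRO score. Report Spearman's coefficient, or the slope of change on change with an intercept, with a 95% CI. If a mixed model is kept, include visit, split each covariate into the woman's mean and her deviation from it, and give the deviation coefficient as the answer. Say separately which model serves objective 2.3.1.

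The cost is a few sentences and no new data. Women with only one visit drop out of this analysis, but they carry no information on change. The intervals will be wide: by Fisher's approximation, a correlation near 0 has 95% limits of about ± tanh(1.96/√22) = ± 0.40 with 25 women and ± tanh(1.96/√12) = ± 0.51 with 15. That width reflects what one change per woman can show.

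### Section 11.4 prescribes semi-parametric bootstrap intervals without stating the resampling scheme; for the mean pH change, coverage is slightly or well below 95% depending on that choice

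*Combined protocol and SAP*

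**What the plan says.** Section 2.3.1 sets the first secondary objective: "To evaluate changes in vaginal pH from the baseline time point to 12 weeks after initiating the VRP". Appendix 1 schedules pH collection twice, at enrollment and at the 12-week visit.

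For the analysis, Section 11.4 says that "linear and generalized linear mixed effects models will be fit to the data gathered", that "The restricted maximum likelihood (REML) criterion will be used", and that "95% semi-parametrically bootstrapped confidence intervals will be obtained for all parameters". The software is R, with no package or function named. The section does not state:

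- whether residuals alone, or residuals and random effects, are resampled;
- whether either is rescaled before resampling;
- whether the interval is percentile, basic or normal.

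On numbers, Section 11.2 says "The first stage sample size will be 15 patients" and, if the trial continues, "a total of 25 patients will be studied". Section 8.2 replaces non-adherent women but still analyses them, so the analysed number can exceed 25.

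**The concern.** A semi-parametric bootstrap of a mixed model keeps the fitted structure and resamples empirical residuals. With two values per woman, her predicted intercept absorbs part of her own measurement error. The residuals left over are therefore systematically smaller than the true errors. Resampling them unadjusted, around fixed intercepts, gives an interval for the visit effect that is too narrow. A larger trial does not cure this, because the number of visits per woman stays at two.

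Vaginal pH is part of the study hypothesis in Section 2.1, and Section 11.4 is the only place in the plan that prescribes confidence intervals. In a single-arm trial the interval for the mean change is the main statement of uncertainty about pH. As written, its width depends on a programming choice that the plan leaves open.

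**Working it through.** **Inputs from the documents.** Two pH values per woman (2.3.1, Appendix 1); n = 15 or 25 (11.2), with n = 30 added to allow for Section 8.2; REML mixed model and nominal 95% level (11.4).

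**Assumptions.** Random-intercept model, normal data, complete pairs, ICC 0.2 to 0.9. The documents give no SD or ICC for pH.

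**The plan's own figure.** The Simon rule (stop at 1 or fewer of 15, reject at 6 or more of 25) has exact type I error 0.0328 at a 10% response rate and exact power 0.8017 at 30%. The stated design reproduces. For pH the only stated figure is the nominal 95%.

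**Size of the raw residuals.** Let σb² and σe² be the between- and within-woman variances. The shrinkage weight of the predicted intercept is

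λ = σb² / (σb² + σe²/2) = ICC / (ICC + (1 − ICC)/2).

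A conditional residual has two parts:

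- plus or minus half the woman's centred difference, with variance σe²/2;
- the unshrunken remainder of her mean, with variance (1 − λ)²(σb² + σe²/2) = (1 − λ)σe²/2.

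The total is σe²(1 − λ/2). With intercepts fixed and raw residuals resampled, the bootstrap SE of the visit effect is therefore too small by the factor sqrt(1 − λ/2).

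Example, ICC 0.5: λ = 0.5/0.75 = 0.667, the factor is sqrt(0.667) = 0.816, and large-sample coverage is 2Φ(1.96 × 0.816) − 1 = 89.1%.

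| ICC | SE factor | Large-sample coverage |
|---|---|---|
| 0.2 | 0.913 | 92.6% |
| 0.3 | 0.877 | 91.4% |
| 0.5 | 0.816 | 89.1% |
| 0.7 | 0.767 | 86.7% |
| 0.9 | 0.725 | 84.5% |

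**Simulated coverage of the mean change** (3,000 trials, 600 resamples each, percentile intervals for the bootstraps):

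| n | ICC | Raw residuals, fixed intercepts | Residuals re-inflated to REML variance | Whole women resampled | Paired t |
|---|---|---|---|---|---|
| 15 | 0.2 | 88.2% | 92.3% | 91.8% | 95.2% |
| 15 | 0.5 | 85.8% | 92.8% | 92.2% | 95.3% |
| 15 | 0.9 | 81.1% | 92.6% | 91.6% | 95.4% |
| 25 | 0.2 | 89.2% | 92.6% | 92.0% | 94.3% |
| 25 | 0.5 | 85.8% | 92.6% | 92.1% | 94.3% |
| 25 | 0.9 | 82.5% | 93.5% | 93.0% | 95.0% |
| 30 | 0.2 | 91.1% | 94.4% | 93.9% | 95.3% |
| 30 | 0.9 | 81.8% | 93.7% | 93.3% | 95.0% |

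Monte Carlo SE is at most about 0.7 points: sqrt(0.81 × 0.19/3000) = 0.007. A repeat simulation reached 80% for the raw scheme at n = 15, hence the range of about 80-91%. Basic and normal intervals behave like percentile ones. Rounding pH to a coarse grid (assumed half a total SD) at n = 25, ICC 0.5 gives 86.9% for the raw scheme.

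**Why re-inflation still falls a little short.** The SE is then about right (ratio 0.98-1.00), but the interval uses in effect a normal multiplier. With 24 degrees of freedom the t multiplier is 2.064, not 1.96, and 1.96 covers 93.8%. With 14 it is 2.145, and 1.96 covers 93.0%.

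**Width.** Paired-t relative to raw-residual width is about (t multiplier/1.96)/(SE ratio). At n = 25 this is 1.053/0.868 = 1.21 at ICC 0.3 and 1.053/0.712 = 1.48 at ICC 0.9. At n = 15, ICC 0.9 it is 1.094/0.703 = 1.56.

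**The case against.** The strongest reply is that the plan does not prescribe the raw-residual scheme. Section 11.4 names no scheme or function, and a bootstrap that re-inflates its residuals is also semi-parametric. That version covers about 92-94%, as well as resampling whole women does, and within one to three points of the paired t. This stands. A reader might infer that the intervals in the plan are bound to cover only some 80-odd percent. The documents do not support that: it needs both the raw scheme and an ICC that they do not give.

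Section 11.4 also describes the pH analysis mainly as relating pH changes to the primary outcome and to PROs. The mean change as target comes from objective 2.3.1. That is a fair reading, but no coverage was computed for the association parameters, and none is claimed here.

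Three further inferences are tempting and should not be drawn:

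- **An inflated 5% test for pH.** The 5% type I error in Section 11.2 belongs to the response rate. No test or decision rule is stated for pH.
- **Badly narrow intervals for the baseline mean.** The baseline mean is not an objective in Sections 2.2 to 2.4.
- **Affected PRO scores.** Section 11.5 summarizes PROs descriptively.

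What the reply does not remove is that each bootstrap simulated falls short of 95% for the mean change, and that the plan leaves open whether the shortfall is small or large.

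**Conclusion.** The point holds in conditional form. With two pH values per woman and 15 to 25 women, the interval method in Section 11.4 is under-specified, and the choice left open matters. Coverage for the mean pH change is about 80-91% with fixed intercepts and raw residuals, and about 92-94% with re-inflated residuals, against a stated 95%. The paired-t interval gives 94-95%.

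These figures rest on normal data, complete pairs, a random-intercept model, ICC 0.2-0.9 and n = 15-30. The direction and mechanism of the raw-residual shortfall do not depend on the exact ICC as long as it is above zero; its size does. The finding concerns the secondary pH endpoint only. The Simon stopping and rejection rules do not use these intervals.

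**What to change.** In Section 11.4, state that the mean change in pH from baseline to 12 weeks will be reported with a paired-t 95% interval on n-1 degrees of freedom. With complete pairs and a positive estimated intercept variance, this is the REML visit effect with the correct degrees of freedom, so the model itself need not change.

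If a bootstrap is kept for other parameters, say what is resampled. Either resample whole women, keeping both visits together, or re-inflate residuals and random effects to their REML variances. Rule out raw conditional residuals, and name the interval type. Whole-woman resampling with percentile limits is not exact at this size (92.0-93.1% at n = 25 for the mean change), so it should not replace the paired t there.

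The cost is one or two sentences and no new data. Intervals widen by about 20-50% relative to the raw-residual version at n = 25 over ICC 0.3-0.9, and by about 56% in the extreme case of n = 15 and ICC 0.9. If re-inflation was always intended, the widening is only about 5-10% (multipliers 2.064/1.96 = 1.05 and 2.145/1.96 = 1.09).
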